8.5	Exploratory Analysis	18
9	Safety Analysis	19
9.1	Adverse Events	19
9.1.1	Adverse Events in the Double-Blind Treatment Period	20
9.1.2	Adverse Events in the Single-blind Placebo Run-in Period	21
9.2	Clinical Laboratory Tests	21
9.2.1	Clinical Laboratory Tests in Double-Blind Treatment Period.....	21
9.2.2	Drug Induced Liver Injury (DILI)	21
9.2.3	Clinical Laboratory Tests in the Single-blind Placebo Run-in Period.....	22
9.3	Vital Signs	22
9.3.1	Vital Signs in the Double-Blind Treatment Period.....	22
9.3.2	Vital Signs in the Single-blind Placebo Run-in Period.....	22
9.4	Electrocardiogram (ECG) Data	22
9.4.1	ECG Data in the Double-Blind Treatment Period	23
9.4.2	ECG Data in the Single-blind Placebo Run-in Period.....	23
9.5	Physical Examinations.....	23
9.5.1	Body Weight, Waist Circumference and Body Mass Index (BMI).....	23
9.6	Suicidality Data	24
9.7	SMWQ.....	24
9.8	Medication Handling Irregularities (MHIs) and Events Subject to Additional Monitoring (ESAMs).....	25
9.9	Concomitant Medications.....	25
9.10	Extent of Exposure	25
10	Conventions	25
10.1	Study Visit Windows.....	25
10.2	Pooling of small centers	26
10.3	Scales: Rules for Scoring and Handling of Missing Data	27
10.3.1	Adult ADHD Investigator Symptom Rating Scale (AISRS).....	27
10.3.2	Clinical Global Impression Severity of Illness Scale – Modified for Attention-Deficit Hyperactivity Disorder	27
10.3.3	Clinical Global Impression Change from Baseline	28
10.3.4	Attention-Deficit Hyperactivity Disorder Impact Module – Adult (AIM-A)	28
10.3.5	Adult ADHD Self Report Scale (ASRS)	28

SAP 405-201-00013

10.3.6	Study Medication Withdrawal Questionnaire (SMWQ).....	28
10.3.7	Columbia-Suicide Severity Rating Scale (C-SSRS).....	29
11	References	30
12	Potential Clinical Relevance Criteria from Protocol	31
13	Proposed List of Summary Tables	34

SAP 405-201-00013

1 Introduction

This statistical analysis plan (SAP) documents the statistical methodology and data analysis algorithms and conventions to be applied for statistical analysis and reporting of efficacy and safety data of study 405-201-00013. All amendments to the protocol are taken into consideration in developing this SAP.

2 Study Objectives

Primary: To confirm the efficacy of centanafadine SR tablets administered BID (200 mg or 400 mg TDDs) compared to placebo in the treatment of adults with ADHD

Secondary: To confirm the safety and tolerability of centanafadine SR tablets administered BID (200 mg or 400 mg TDDs) compared to placebo in the treatment of adults with ADHD

3 Study Design

This trial is a phase 3, randomized, double-blind, multicenter, placebo-controlled, parallel-group trial to confirm the efficacy, safety, and tolerability of centanafadine SR (200 mg TDD or 400 mg TDD) compared to placebo for the treatment of adults with ADHD. The trial population will include male and female subjects 18 to 55 years of age (inclusive) with a current diagnosis of ADHD as confirmed by the Adult ADHD Clinical Diagnostic Scale (ACDS) Version 1.2 at screening.

The trial will have 4 periods: (1) screening and washout; (2) 1 week single-blind placebo run-in; (3) 6-week double blind treatment; and (4) 7-day follow-up period (follow-up telephone calls at 1, 3, and 5 days after the last dose of IMP, and in-clinic visits 2 and 7 days after the last dose of IMP) for subjects who complete the trial, and decide to enroll in Trial 405-201-00015. For subjects who terminate early, decide to not enroll in Trial 405-201-00015, or who are not eligible to enroll in Trial 405-201-00015, they will be required to participate in the 7-day follow-up period as well as participate in an additional follow-up telephone call 10 days after the last dose of IMP. Subjects randomized to receive a TDD of 200 mg centanafadine SR will start at their target dose at the start of the double-blind treatment period. Subjects randomized to receive a TDD of 400 mg centanafadine SR will start the double-blind treatment period at the TDD of 200 mg centanafadine SR for 7 days, before they are escalated to their target TDD of 400 mg for a total of approximately 42 days of treatment. Subjects will be required to visit the site up to 12 times over the trial. See [Figure 3-1](#) for a schematic of the trial design.

Subjects who complete both the 6-week double-blind treatment period and the 7-day safety follow-up period (follow-up telephone calls at 1, 3, and 5 days after the last dose of IMP, and in-clinic visits 2 and 7 days after the last dose of IMP), and refrain from using prohibited

SAP 405-201-00013

medications after the IMP is stopped may be eligible to enroll into Trial 405-201-00015, which is a 12-month, observational, open-label trial to evaluate the long-term safety and tolerability of subjects with ADHD who previously participated in Trials 405-201-00013 or 405-201-00014. Subjects who terminate early, decide to not enroll in Trial 405-201-00015, or who are not eligible to enroll in Trial 405-201-00015, will be required to participate in the 7-day follow-up period as well as participate in an additional follow-up telephone call 10 days after the last dose of IMP. For subjects who early terminate or decline participation in the open-label trial, they will be instructed to refrain from utilizing prohibited concomitant medications, including ADHD treatments, until after the follow-up telephone call 10 days after the last dose of IMP.

[figure not shown]

Figure 3-1 Trial Design Schematic

ASRS = Adult ADHD Self Report Scale; CTN SR = centanafadine sustained release; ET = early termination; P = placebo administration; R = randomization.

^aAll subjects will be required to participate in the 7-day follow-up period (follow-up telephone calls at 1, 3, and 5 days after the last dose of IMP, and in-clinic follow-up visits at 2 and 7 days after the last dose of IMP). Subjects who terminate early, decide to not enroll in Trial 405-201-00015, or who are not eligible to enroll in Trial 405-201-00015, will be required to participate in an additional follow-up telephone call 10 days after the last dose of IMP.

During the trial, administration of the investigational medicinal product (IMP) will be double-blinded. In other words, neither the investigator nor the subject will have knowledge of the treatment assignment (e.g., centanafadine SR 200 mg, 400 mg, or placebo). Treatment assignments will be based on a computer-generated randomization code provided by the Otsuka Pharmaceutical Development & Commercialization, Inc (OPDC) Biometrics Department. Sponsor personnel, including those involved in monitoring, data management, and data analysis, will not have access to the treatment code during the trial. The bioanalytical

SAP 405-201-00013

laboratory will also be sent the randomization code. The randomization will be stratified by trial site and designed to allocate subjects in a 1:1:1 ratio to centanafadine SR 200 mg/day or 400 mg/day or placebo.

4 Sample Size and Power Justification

The primary efficacy endpoint is the change from baseline at Day 42 in Adult ADHD Investigator Symptom Rating Scale (AISRS) total score. The trial will compare the placebo arm to the centanafadine dose arms, randomized at a ratio of 1:1:1, with an overall alpha of 0.05 for the primary endpoint.

Based on the results from Phase 2 centanafadine trials, it is reasonable to expect a treatment effect of 5 points with a standard deviation (SD) of 12.5 in the mean change from baseline to Day 42 on AISRS total score. The planned sample size of 405 evaluable subjects (135 in each treatment arm) will yield at least 90% power to detect the treatment effects at a 2-tailed significance level of 0.05.

A sufficient number of subjects will be enrolled and randomized to achieve approximately 405 evaluable subjects in the Double-blind Treatment Phase (i.e., subjects with an AISRS total score at baseline and at least 1 subsequent AISRS total score in the Double-blind Treatment Phase). After allowance of 10% non-evaluable subjects in the Double-blind Treatment Phase, the total number of subjects to be randomized is 450 (150 in each treatment arm). In order to ensure 405 evaluable subjects, the number of non-evaluable subjects will be monitored in a blinded manner on an ongoing basis During the trial. The power and sample size were obtained using the PASS 14 (2015) statistical computing software.

5 Data Sets for Analysis and Missing Data

5.1 Data Sets for Analysis

The following analysis samples are defined for this trial:

Enrolled Sample: comprises all subjects who signed an informed consent form (ICF) for the trial and enrolled into the single-blind placebo run-in period.

Randomized Sample: comprises all subjects who were randomized in the double-blind treatment period. Subjects are considered randomized when they are assigned a treatment group by eSource at the end of single-blind placebo run-in period. A subject receiving IMP outside of the eSource will not be considered randomized, but safety will be reported.

Safety Sample: comprises those randomized subjects in the double-blind treatment period who received at least one dose of double-blind IMP as indicated on the dosing record. Subjects will only be excluded from this population if there is documented evidence (i.e., drug

SAP 405-201-00013

dispensed = drug returned or no IMP dispensed) that the subject did not take IMP. If a subject is dispensed IMP and is lost to follow up, he/she will be considered exposed.

Efficacy Sample: the Full Analysis Set (FAS) comprises all subjects in the Safety Sample who have a baseline value and at least one valid post-randomization efficacy evaluation for AISRS total score in the double-blind treatment period.

Per Protocol (PP) Sample: comprises those subjects in the Efficacy Sample who complete at least the first 2 weeks of double-blind medication ((last day of IMP - first day of IMP + 1) \geq 14 days) and have at least one post baseline AISRS measurement on or after Day 14 visit during the double-blind treatment period without major protocol violations deemed to compromise the assessment of efficacy. These major protocol violations will be any of the followings:

1. Subjects who were not at least 80% or were more than 120% compliant with double-blind IMP or missed 7 or more consecutive days of dosing immediately prior to the Day 42/ET AISRS measurement date during the double-blind treatment period based on subject-reported (eCRF) compliance data
2. Subjects who reported concomitant medication use that will impact the primary efficacy endpoint
3. Subjects who had major protocol deviation as represented on the protocol deviation eCRF page that will impact the primary efficacy endpoint
4. Subjects who took the wrong study treatment

The core dataset for all efficacy analyses is the FAS, which is created based on the intent-to-treat (ITT) principle. However, as will be described below, in order to handle missing data and restrictions imposed by different types of analyses (e.g., change from baseline analysis), other datasets derived from the FAS dataset will be used for the efficacy analyses.

5.2 Handling of Missing Data

The mixed-effect model repeated measure (MMRM) assumes data are missing at random (MAR), which is a reasonable assumption in longitudinal clinical trials in MDD¹. However, the possibility of “missing not at random” (MNAR) data can never be ruled out. As sensitivity analyses, selection model², pattern-mixture model^{3,4,5,6}, and/or shared parameter model⁷ will be used to explore data missing mechanisms of MNAR and investigate the response profile of dropout patients by last dropout reason under MNAR mechanism for the following 3 scenarios: 1) Dropout reasons due to either AE or LOE as MNAR, 2) Dropout reasons due to either AE or LOE or subject withdrew consent as MNAR, 3) All dropouts as MNAR using

SAP 405-201-00013

both 1) Delta adjustment imputation method which is to departure from MAR assumption by progressively increasing the delta until conclusion from the primary analysis is overturned, and 2) Placebo based imputation methods in which missing data for both placebo and drug group are imputed based on the imputation model derived from placebo data. If drug improved outcomes prior to dropout, this benefit is carried into subsequent imputed values, but will diminish over time in accordance with the correlation structure. Details are provided in [Section 8.1.3](#) Sensitivity Analysis.

The observed-cases (OC) data set will consist of actual observations recorded at each visit during the double-blind treatment period and no missing data will be imputed. MMRM, Wu-Bailey, and pattern-mixture model will be performed on the OC dataset.

The last-observation-carried-forward (LOCF) data set will include data recorded at a scheduled double-blind treatment period visit or, if no observation is recorded at that visit, data carried forward from the previous scheduled double-blind treatment period visit. Baseline data (e.g., the last visit of the single-blind placebo run-in period) will not be carried forward to impute missing values for the LOCF data set. The analysis of covariance (ANCOVA) analysis will be performed for the change from baseline to the end of the double-blind treatment period (Day 42, LOCF) in AISRS total score as sensitivity analysis. The ANCOVA_LOCF model includes treatment and study center as main effects, and baseline value as a covariate.

ANCOVA analysis with OC data will also be conducted on change from baseline for AISRS total score, as well as all continuous change from baseline efficacy endpoints.

For Clinical Global Impression (CGI) Change from Baseline and categorical response/remission variables, OC analyses will be performed in addition to LOCF analyses. Study center will not be included in the models for OC analyses.

6 Study Conduct

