treatment difference between centanafadine and Placebo from the primary analysis of MMRM model until conclusion of the primary analysis is overturned. When $\delta=0$ it is MAR. When $\delta > 0$ it is MNAR.

- 1) Using Monte Carlo Markov Chain (MCMC) methodology from PROC MI to impute the intermittent missing data to a monotone missing pattern;
- 2) Using a standard MAR-based multiple imputation approach from PROC MI to impute the monotone missingness data
- 3) For patients in the treated group and with a dropout reason of AE or LOE or subject withdrew consent, a delta will be added for all the values after the dropout time.
- 4) Using MMRM model in the primary analysis to analyze the completed data using PROC MIXED on the multiple imputed data
- 5) Obtaining the overall results using PROC MIANALYZE.

Placebo Based Imputation Methods

Similar to “Standard” multiple imputations, except parameters for imputation model obtained from only the placebo (control) group. Missing data for both placebo and drug group are imputed based on the imputation model derived from placebo data. If drug improved outcomes prior to dropout, this benefit is carried into subsequent imputed values, but will diminish over time in accordance with the correlation structure.

In addition, model based MNAR methods such as the shared parameter model (Wu and Bailly, 1989) and random coefficient pattern mixture model (Hedeker D, Gibbons RD, 1997) will be also performed.

LOCF and OC Analyses

Change from baseline of the double-blind treatment period for the AISRS total score will be evaluated using ANCOVA with baseline of the double-blind treatment period value as covariate and treatment and, in LOCF analyses, study center as main effects. For the OC analyses, study center will not be included in the model.

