8.1.4 Subgroup Analyses

Subgroup analyses of change from baseline of the double-blind treatment period in AISRS total score to every scheduled visit in the double-blind treatment period will be performed by the following factors:

- Sex (Based on the biological status)
- Race (White and All Other Races)

All subgroup analyses will be conducted using the same MMRM analysis as for the primary efficacy analysis except that the fixed class effect term for trial center will not be included in the model.

Interaction effects of treatment-by-subgroup will be assessed at Day 42 for the subgroups identified in the previous paragraph. MMRM analyses will be performed by adding addition of terms for subgroup-by-day and treatment-by-subgroup-by-day. These treatment-by-subgroup interaction analyses will be presented in statistical documentation.

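### The OC ANCOVA and OC CMH tests drop the centre term that the LOCF versions keep, so the OC-versus-LOCF comparison changes the model as well as the data set (minor)

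*SAP*

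**What the plan says.** On the design, SAP section 3 states: "The randomization will be stratified by trial site". Protocol 3.6.1 agrees.

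Pooled centre is kept in:
- the primary MMRM, fitted to OC data (SAP 8.1.1 and 8.1.2), and the analyses that reuse it, including the key secondary CGI-S analysis (8.2);
- the LOCF ANCOVA (5.2 and 8.1.3.1);
- the LOCF CMH tests (8.3).

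Centre is dropped from:
- the OC ANCOVA: "For the OC analyses, study center will not be included in the model" (8.1.3.1). Section 5.2 extends OC ANCOVA to all continuous change-from-baseline efficacy endpoints;
- the OC tests for CGI Change, response and remission: "Study center will not be included in the models for OC analyses" (5.2), repeated in 8.3. Protocol 7.3.2.2 already specified this for CGI Change and the responder rate;
- the by-subgroup MMRMs, where the "fixed class effect term for trial center will not be included in the" model (8.1.4).

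No reason is given in any of these places. The sentence in 5.2 follows one about CGI Change and the categorical variables. Read alone, it would contradict the primary MMRM, which is an OC analysis with centre.

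**The concern.** The OC and LOCF ANCOVAs are presented as a pair, so that a reader can see how the answer depends on the handling of missing data. That reading requires everything except the data set to stay fixed. Here the centre term changes too, and any difference between the two results could come from either source.

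There is also a mismatch with the design. An analysis that ignores a stratification factor does not use the balance that stratification created. OC data at Day 42 are the subset still observed, 109, 119 and 119 subjects in the 200 mg, 400 mg and placebo arms (STAT-4.7), so site balance is no longer assured.

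At stake is how a set of sensitivity and nominal-level analyses is interpreted. The confirmatory tests are not involved.

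**Working it through.** **1. A pair of tables that isolates centre.** STAT-4.2 (treatment, pooled centre, baseline) and STAT-4.3 (treatment, baseline) both use 438 records, with arm means -9.973, -9.857 and -7.458 for 200 mg, 400 mg and placebo. Only the centre term differs. STAT-5.2 and STAT-5.3 form the same kind of pair for CGI-S, with 437 records.

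**2. Reproducing the printed standard errors.** SE = sqrt(MSE) × design factor.
- Without centre the design factor is sqrt(1/147 + 1/144) = 0.11725. So sqrt(114.405) × 0.11725 = 1.2541; printed 1.2541.
- With centre, the arm counts of the 38 pooled centres in STAT-4.5.1 give 0.11784 for 200 mg. So sqrt(110.525) × 0.11784 = 1.2389; printed 1.2389.

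**3. What dropping centre does.**

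| Contrast with placebo | Estimate, with → without | SE, with → without | SE ratio | p, with → without |
|---|---|---|---|---|
| AISRS 200 mg | -2.73 → -2.50 | 1.2389 → 1.2541 | 1.012 | 0.0284 → 0.0469 |
| AISRS 400 mg | -2.27 → -2.39 | 1.2395 → 1.2541 | 1.012 | 0.0674 → 0.0572 |
| CGI-S 200 mg | -0.2095 → -0.2005 | 0.10853 → 0.10797 | 0.995 | 0.0543 → 0.0641 |
| CGI-S 400 mg | -0.2183 → -0.2297 | 0.10827 → 0.10777 | 0.995 | 0.0445 → 0.0336 |

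**4. Estimate or standard error?** Hold the AISRS SE at its with-centre value (397 df) and change only the estimate:
- 200 mg: -2.4987/1.2389 = -2.017, p = 0.044. This is most of the move from 0.028 to 0.047.
- 400 mg: -2.3915/1.2395 = -1.929, p = 0.054. The larger SE then brings it back to 0.057.

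The p-values therefore move mainly because the estimates move.

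**5. Why the estimates move.** STAT-4.5.2 shows one centre with 9, 13 and 12 subjects (200 mg, 400 mg, placebo) and mean changes -27.56, -15.62 and -15.42.
- Its overall mean is -636.14/34 = -18.7.
- The other 404 subjects average (-3989.0 + 636.1)/404 = -8.3, a gap of -10.4.
- The centre holds 9/147 = 6.1% of the 200 mg arm and 12/144 = 8.3% of placebo.
- Unadjusted, this shifts the 200 mg contrast by about (0.0612 - 0.0833) × (-10.4) = +0.23. The observed shift is -2.499 + 2.725 = +0.23.

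This is approximate, because other centres also contribute and the centre mean contains treatment effect. For 400 mg the same sum gives -0.05 against an observed -0.12.

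**6. Why the precision effect is mixed.** Dropping centre raises the residual SD but improves the design factor (0.11725/0.11784 = 0.995).
- AISRS: sqrt(114.405/110.525) = 1.017, and 1.017 × 0.995 = 1.012. Centre has F = 1.41, p = 0.060.
- CGI-S: sqrt(0.8447/0.8432) = 1.001, slightly more than offset by the design factor. Centre has F = 1.02, p = 0.44.

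**7. The OC label.** STAT-4.7 gives 109 + 119 + 119 = 347 subjects observed at Day 42, and STAT-4.9 also has 347. STAT-4.3 is titled OC but has 438 records, and its arm means equal the Day 42 LOCF means in STAT-4.6. The true OC means are -10.83, -10.89 and -7.78. STAT-5.3 raises the same question.

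**The case against.** The strongest reply is that little depends on this. The analyses are sensitivity or nominal-level. The primary and key secondary tests are centre-adjusted on OC data. The CMH choice was already in the protocol. Omitting a prognostic stratification factor tends to make inference conservative. All of this stands, and it is why the point is minor.

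Three stronger readings are tempting, and the documents do not support them.

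- A reader might infer that omitting centre gives needlessly wide intervals throughout. The paired output shows +1.2% for AISRS and -0.5% for CGI-S. The p-values are no evidence either: without centre the 400 mg AISRS p-value falls. The MMRM centre effect is stronger (F = 2.25, p < 0.0001), but that model keeps centre. For a true Day 42 OC ANCOVA, assuming an intra-centre correlation of 0.2% to 8%, the expected interval width without centre relative to with centre is 0.98 to 1.02. For the OC CMH test, assuming response of 25% vs 40% or 35% vs 50%, mean z differs by less than 0.1 between versions.
- A reader might infer that every OC model drops centre. The primary MMRM does not, nor do the analyses that reuse it for other endpoints.
- A reader might want the 38-level centre term in the by-subgroup MMRMs as well. Pooling assures one evaluable subject per arm in the whole Efficacy Sample, not within a subgroup. The sex and race interaction models (STAT-3.1, STAT-3.2) did run with centre, but on all 438 subjects. Assuming half the sample per sex and 16% in All Other Races, with the same correlation range, leaving centre out gives the narrower interval: ratios 0.95 to 0.99 and 0.78 to 0.82.

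**Conclusion.** The point holds as one of consistency and interpretability. Centre is omitted from the OC ANCOVA and OC CMH tests without a reason, while their LOCF counterparts keep it. An OC-versus-LOCF difference therefore cannot be attributed to missing-data handling alone. On identical records the centre term by itself moves the AISRS estimates by 0.23 (200 mg) and 0.12 (400 mg) points, enough to change p-values close to 0.05. The change in precision is about 1% or less in either direction. No confirmatory result is affected. Severity: minor.

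The size comes from LOCF-size data, because the table labelled OC holds 438 records. It shows what the centre term does, not what a correct OC ANCOVA on 347 subjects would give. The output does not show how far the OC CMH results would move; the ranges given for them rest on assumed response rates and correlations.

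**What to change.** 1. Include pooled centre as a main effect in the OC ANCOVAs, as in the LOCF model.
2. Show the OC CMH tests stratified by pooled centre beside the unstratified version already specified.
3. Limit the centre sentence in SAP 5.2 to the analyses it is meant for, so that it cannot be read as covering the MMRM.
4. Leave the by-subgroup MMRMs without the 38-level term, and state the reason.
5. Check the input data for STAT-4.3 and STAT-5.3, and correct the label or rerun on observed Day 42 records.

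The cost is SAP wording and a rerun. The ANCOVAs spend up to 37 degrees of freedom, and CMH strata with an arm missing at a visit contribute little or nothing. The appended output (18 June 2020) is later than the SAP signatures (27 April 2020), so anything added now should be labelled as added after the results.
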